3.1.2 Biochemical progression (rising PSA) after medical or surgical castration

- Subjects who have received antiandrogens (such as bicalutamide) and have experienced PSA decline must have biochemically (PSA) progressed following discontinuation of anti-androgen therapy.
- **PSA:** An increase in PSA determined by two separate measurements taken at least one week apart and confirmed by a third, and if necessary, a fourth measurement. If the third measurement is not greater than the second measurement, then a fourth measurement must be taken; the fourth measurement must be greater than the second measurement for the patient to be eligible for enrollment in the study. Furthermore, the confirmatory PSA measurement (i.e., the third or, if applicable, fourth PSA measurement) must be ≥ 1 ng/mL with prior prostatectomy or ≥ 2 ng/mL without prostatectomy and $\geq 25\%$ above the previous nadir.

3.1.3 High risk of systemic progression defined as:

- Rising PSA as defined above and either:
 - Absolute PSA > 20 ng/mL
AND/OR
 - PSA DT < 8 months

PSA doubling time (PSA-DT) will be calculated using a linear regression model. In the model, the logarithm of PSA will be modeled as a linear function of time. The PSA-DT will be calculated as the product of $\log 2$ multiplied by the reciprocal of the slope of the regression equation, for which the logarithm is the natural log function. For standardization purposes across sites, a web-based PSA doubling time calculator developed by Memorial Sloan Kettering, is available at <http://www.mskcc.org/mskcc/html/10088.cfm>

The minimum PSA value for eligibility will be greater than or equal to 1 with prior prostatectomy or at least 2 ng/mL without prostatectomy. All PSA values of at least 0.1 ng/mL over the past 6 months must go into the equation. A minimum of 3 PSA values with a minimum of 2 weeks between assessments is required (the screening PSA may be used for the 3rd value if necessary).

- 3.1.4 No evidence of local recurrence or distant metastases within 1 month of enrollment (or following enrollment as part of screening) including:
 - Radionuclide bone scan without evidence of metastatic disease
 - In the event of an equivocal bone scan, confirmation is needed with Xray, CT scan, or MRI
 - CT or MRI of abdomen/pelvis without evidence of metastatic disease or recurrent disease in the prostate or prostate bed

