10.1 STUDY PROCEDURES: Schedule of Events

The assessments to be performed during the study are outlined below by study period, visit and day. Study assessments through Visit 9 (Day 85) will be completed within ± 3 days of the specified day for the visit, except where noted. Visits after Day 169 will be performed within ± 7 days of the scheduled visit.

Screening Period (Visit 1, Days -28 to -1) – All subjects

The procedures outlined for Visit 1 must be completed prior to the patient receiving study drug. The following procedures will be conducted at Visit 1:

- Informed Consent
- Medical History
- Concurrent medications
- Complete Physical Exam
- Vital Signs
- Demographics
- Previous therapy
 - Surgical report will include date and type of surgery +/- lymphadenectomy
 - Radiotherapy report will include modality of therapy with prescribed dose and field and dates of therapy
 - Previous hormonal therapy – drugs, doses, dates of therapy
 - Continuous vs intermittent therapy
- ECOG Performance Status
- Height, Weight
- CBC with differential and platelet count.
- PT or INR, PTT
- Electrolytes, BUN, Creatinine
- Total protein, albumin, calcium, total bilirubin, AST, ALT, LDH
- PSA
- PSA DT Calculation

- Alkaline phosphatase
- Testosterone
- Human anti-J591 antibody sample (may also be drawn C1D1 prior to initiation of study drugs)
- Urinalysis
- Archival Tissue (section 9.1.4) - Paraffin-embedded tumor blocks or 5 unstained slides with representative tumor tissue
- EKG, up to 1 month prior to treatment
- CT or MRI (abdomen-pelvis), up to 4 weeks prior to enrollment
- Bone scan, up to 4 weeks prior to enrollment
 - Any confirmatory tests to assess equivocal results of bone scan should also be completed within 4 weeks of enrollment
 - CXR, up to 4 weeks prior to enrollment (if CT chest has been performed within 4 weeks of enrollment, this procedure is waived)

Evaluations and procedures at Visit 2 (C1D1) – All subjects

Following screening procedures, eligible patients will be dosed with ketoconazole and hydrocortisone. See Section 5.1 for details on the dose and administration.

The following assessments are to be collected prior to drug administration unless otherwise noted:

- Interval medical history
- Targeted Physical Examination with vital signs
- ECOG PS
- CBC with differential and platelet count*
- Electrolytes, BUN, Creatinine*
- PSA*
- Adrenal hormone levels
- Plasma markers
- CTC's
- Adverse Events

- Concomitant medications

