13. STATISTICAL CONSIDERATIONS

13.1 Study Design/Endpoints

The study is a randomized phase 2 study with a 2:1 ratio favoring ^{177}Lu -J591, with stratification by investigational site and mode of primary therapy (radiation vs surgery). Randomization will be performed by using a series of randomized blocks of 6 within each participating site/primary therapy stratum (with a 2:1 allocation ratio). This will provide assurance that after six patients are enrolled in any given participating site/primary therapy stratum, there will be four patients assigned to the combination regimen (Group 1) and two patients assigned to the single regimen (Group 2). This procedure will allow for each site to contribute similar numbers of ^{177}Lu -J591/ketoconazole patients and ^{111}In -J591 (placebo)/ketoconazole patients within the defined participating site/primary therapy strata.

The primary endpoint is the proportion free of metastases in each group at 18 months. Ninety-five percent confidence intervals (95% CI) will be estimated for the 18-month MFS proportion in both groups via binomial proportions. The MFS proportion will also be descriptively evaluated at 12, 24, 30, and 36 months in each group.

MFS will be measured from the start of the treatment to the date of either documentation of metastatic disease or death. All treated patients will be observed for a minimum of 18 months. The 18-month MFS proportion with ketoconazole + ^{111}In -J591 has been estimated to be 50% {521 Smith, M.R. 2005}; therefore, the target 18-month MFS proportion for the combination of ketoconazole + ^{177}Lu -J591 regimen is hypothesized to be 80%. An intent to treat analysis will include all randomized subjects. However, we will also analyze subjects who received study-drug. This subset will be those subjects who met eligibility requirements, have initiated therapy, and were not removed from the study for non-compliance or patient withdrawal within the first 4 weeks, and received infusion of study drug.

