With approximately 34 patients in the ketoconazole+J591 arm and 17 patients in the ketoconazole monotherapy arm (2:1 allocation), this design will allow for the detection of a 30% absolute difference in the 18-month MFS proportion between the ketoconazole+J591 arm and the ketoconazole monotherapy arm (80% vs. 50%, respectively) with $\geq 80\%$ power and a one-sided alpha level of 10%. An additional 10% will be enrolled to account for loss to follow up (total projected number of subjects to be randomized = 55). A 95% CI for the difference in the 18-month MFS proportion between the two treatment arms can be constructed to be within $\pm 18\%$ of the true difference in 18-month MFS proportions.

13.1.1 ^{111}In -J591 as placebo

We have chosen to infuse ^{111}In -J591 as a placebo in this double-blind study. The infusion procedures and characteristics of this compound are similar to ^{177}Lu -J591. In addition, ^{111}In -J591 will allow imaging studies to be performed. Because ^{111}In is a pure gamma-emitter, there will be no treatment effect as in the beta emission with ^{177}Lu . It is theoretically possible that by infusing ^{111}In -J591, there will be a treatment effect by ADCC, thereby diluting the proportional effect of ^{177}Lu -J591 in the experimental arm. However, clinically meaningful ADCC is not expected, as it has been demonstrated at

much higher doses of the J591 antibody (122), and by giving equal antibody doses in each study arm, we will be able to truly evaluate the effect of ^{177}Lu radioimmunotherapy.

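### The 18-month comparison uses neither the primary-therapy randomisation factor nor screening PSA doubling time; prespecified adjustment would be a cheap improvement, not the repair of an error

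*Combined protocol and SAP*

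**What the plan says.** Section 13.1 sets a binary primary endpoint: "The primary endpoint is the proportion free of metastases in each group at 18 months". The estimation sentence is "Ninety-five percent confidence intervals (95% CI) will be estimated for the 18-month MFS proportion in both groups via binomial proportions". For the contrast between arms, the same section says "A 95% CI for the difference in the 18-month MFS proportion between the two treatment arms can be constructed to be within" 18 points of the true difference. It gives at least 80% "power and a one-sided alpha level of 10" percent, for 80% versus 50% metastasis-free with 34 and 17 men. No primary test is named, and no stratified or regression analysis of this endpoint appears anywhere in section 13.

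The design does use baseline information elsewhere. Randomisation is in blocks of six "with stratification by investigational site and mode of primary therapy (radiation vs surgery"). Section 3.1.3, under "High risk of systemic progression defined as", requires PSA above 20 ng/mL and/or PSA-DT below 8 months, and asks for at least three PSA values. The screening visit in section 10.1, which applies to all subjects, lists "PSA DT Calculation".

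**The concern.** The trial turns on one comparison with 17 controls and, under its own assumptions, about 15 events. The protocol treats PSA level and PSA-DT as markers of the risk being measured, but PSA-DT is neither a stratification factor nor an analysis covariate. Any chance difference in PSA-DT between the arms therefore stays in the estimated effect. Primary therapy is balanced by design and then dropped from the analysis. If these variables are prognostic, a more precise estimate is available from data already collected. Adjustment would have to be fixed in advance, because adjusting only after an imbalance is seen would not be credible.

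**Working it through.** **Inputs.** From 13.1: 34 versus 17 men; control metastasis-free proportion "has been estimated to be 50" percent; target 80%; one-sided alpha 0.10. Number of sites (10–16): protocol summary. The prognostic strength of PSA-DT is not in the documents, so it is assumed over a range.

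**1. The plan's own power.** The pooled proportion is (17 × 0.5 + 34 × 0.8)/51 = 0.70.
- Null SE = √[0.70 × 0.30 × (1/17 + 1/34)] = 0.136.
- Alternative SE = √(0.25/17 + 0.16/34) = 0.139.
- Power = Φ[(0.30 − 1.2816 × 0.136)/0.139] = 81.6%.

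The stated figure reproduces as an unadjusted, uncorrected two-proportion z-test. The 95% half-width at this SE is 1.96 × 0.139 = 27.3 points, not 18. That is a separate discrepancy, and adjustment would not close it: the covariates would have to explain 1 − (18/27.3)² ≈ 57% of the outcome variance.

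**2. Events.** 0.2 × 34 + 0.5 × 17 = 15.3.

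**3. Chance imbalance.** For a continuous baseline value outside the randomisation, the SE of the standardised difference is √(1/34 + 1/17) = 0.297 SD. The arms differ by more than 0.3 SD in about 31% of trials and by more than 0.5 SD in about 9%. In simulation with assumed log-odds slopes of 0.8–1.5 per SD, the crude risk difference moves 16–25 points per SD of imbalance. A 0.5 SD imbalance therefore moves it by 0.5 × 16 = 8 to 0.5 × 25 = 12.5 points, against a 30-point target. The adjusted estimate moved by about 1 point or less per SD.

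**4. Effect of adjustment.** Simulation of a two-term model (arm, a binary primary-therapy term, one continuous covariate), 34 versus 17, 3,000 runs per scenario, Firth-logistic test for arm at one-sided 10%:

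| Assumed slope (log-odds per SD) | Crude power | Adjusted power | SD of risk difference, unshrunk adjustment (crude about 14) |
|---|---|---|---|
| 0 (not prognostic) | 82–83% | 79% | – |
| 0.8 | 82–83% | 82% | 13.3 points |
| 1.1 | 82–83% | 85% | 12.8 points |
| 1.5 | 82–83% | 89% | 12.2 points |

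Monte Carlo error is about √(0.82 × 0.18/3000) = 0.7 points, so the 0.8 row shows no power gain. Type I error of the Firth test was 9–10%.

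As a cross-check, scaling the variance by (1 − R²) gives 84.6% power at R² = 0.10 (SE 13.2 points) and 87.6% at R² = 0.20 (SE 12.5 points).

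**5. What belongs to shrinkage.** A Firth model narrows the risk difference even with a useless covariate: the SD falls from 14.1 to 13.3 points while the mean effect falls from 29.9 to 28.6. The unshrunk column above is therefore the fair measure of the precision gained.

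**6. Choice of interval and test.** A standardised risk difference with influence-function standard errors gave type I error of 0.102–0.119 against a nominal 0.10.

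**7. Site.** Ten to 16 sites by two therapy levels make 20–32 cells, or 55/20 = 2.75 down to 55/32 = 1.7 men per cell. Site cannot be a model term with about 15 events.

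**The case against.** The strongest reply is that nothing in the plan is wrong. Under randomisation the crude difference is unbiased, chance imbalance is already counted in its standard error and type I error, and the stated power is met. All of that stands.

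A reader might infer that omitting the stratification factor makes the error bars wrong in a harmful direction. The documents do not support that. If the stratum is prognostic, the crude interval would normally be conservative; if it is not, nothing changes.

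Three further objections stand in part:
- The quoted interval sentence concerns each arm separately. That the comparison itself is crude is inferred from the difference and power statements and from the absence of any other method.
- The unnamed test matters more for power than the covariates may. By exact enumeration at 34 versus 17, the uncorrected z-test has 82.4% power and Fisher's exact test 73.1%.
- An entry cut-off does not show that PSA-DT is prognostic among men already selected on PSA, and the value may rest on only three measurements.

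The therapy term also cannot be coded as the text stands. The protocol summary and 13.1 contrast radiation with surgery; 13.3 contrasts any local treatment with none; and 3.1.4 provides for men who have had neither. These points limit the claim and shape the remedy. They do not remove the case for using a pre-randomisation value that is already scheduled for every man.

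**Conclusion.** The point holds as a recommended improvement. The planned comparison is valid and adequately powered on its own terms (about 82%), and it leaves available baseline information unused. Prespecified adjustment would take power from about 82–83% to about 82–89% and the SD of the risk difference from about 14 to about 12–13 points without shrinkage. Firth estimation narrows it further, but pulls the estimate in by 1–2 points. The more dependable benefit is protection of the single primary estimate from chance PSA-DT imbalance.

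These sizes rest on assumed slopes of 0.8–1.5 per SD. If PSA-DT is unrelated to metastasis in this population, adjustment costs about 3–4 points of power and leaves about 79%, just under the 80% target. It would be too strong to conclude that the sample size is wrong or that a crude result would be untrustworthy.

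**What to change.** 1. Reconcile the primary-therapy stratum across the protocol summary, 13.1 and 13.3, including where men with no local treatment belong.
2. In 13.1, before unblinding, prespecify an adjusted between-arm analysis with arm, primary therapy as randomised and log PSA-DT at screening, without site. State how a flat or negative PSA slope is coded, since log PSA-DT is then undefined.
3. Name the test: a one-sided 10% Firth-logistic test for arm, or a permutation test.
4. Report the standardised 18-month risk difference with a named small-sample interval, for example a bootstrap, rather than influence-function standard errors.
5. Keep the crude proportions and their difference as a sensitivity analysis.

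The cost is analysis-plan wording and one model. No extra patients, visits or data are needed. The risk is the 3–4 points of power noted above if PSA-DT is uninformative.

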A subsequent multicenter phase I/II study was initiated based upon the above results (50). Sixty two subjects received multiple doses of MLN2704. Because of neurotoxicity at every 1 or 2 week doses, the study was amended to include every 3 week dosing and dosing on days 1 and 15 of 42-day cycles. Of the 4 schedules tested, PSA declines were most frequent at 330 mg/m² every 2 weeks (2/6 had PSA decrease $>50\%$, 2/6 had PSA stabilization). However, grade 2-3 neuropathy was dose-limiting, and could not be predicted by prior taxane-based chemotherapy, diabetes, or prior neuropathy. Although response was modest, and treatment was limited by toxicity, this trial demonstrated proof of principle that an immunoconjugate utilizing a PSMA antibody has therapeutic potential.

Phase II trial of ¹⁷⁷Lu-J591 in metastatic castrate resistant prostate cancer

Based upon the phase I results described above (47), a phase II trial has completed enrollment. In this investigator-initiated study, subjects with progressive metastatic CRPC received one dose of ¹⁷⁷Lu -J591 in two-cohorts. Cohort 1 (65mCi/m²), 15 pts; Cohort 2: (70mCi/m²), 17 pts. The primary endpoint is PSA and/or measurable disease response; the secondary endpoint is toxicity. A ¹⁷⁷Lu-J591 imaging study was done to confirm tumor targeting.

All of the initially planned 32 pts (14 chemo-naïve) have been treated. Preliminary analysis reveals the following (51):

Median age is 71 (range 51 – 88), median baseline PSA 77.92 (range 3.31 – 2184.6). Three pts achieved PSA declines of >50%. Another more preliminary analysis has been performed based upon retrospective analyses in patients on prospective chemotherapy trials demonstrating that 30% declines in PSA are most associated with survival benefits (52, 53). Of the 15 subjects receiving 65mCi/m², 2 of 15 (13%) achieved a 30% PSA decline. Of the 17 subjects receiving 70mCi/m², 7 (47%) experienced at least a 30% decrease in PSA.

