13.4 Analysis of Secondary & Exploratory Endpoints

Secondary endpoints include biochemical (PSA) response rate, duration of PSA response, biochemical (PSA) progression, time to biochemical (PSA) progression, time to biochemical (PSA) progression above baseline, overall survival, and toxicity. We anticipate that the 95% confidence interval around the PSA response rate will be within $\pm 9\%$ of the true value for Arm 1 and within $\pm 15\%$ of the true value for Arm 2. Time to biochemical (PSA) progression, time to biochemical (PSA) progression above baseline, median MFS-time, and overall survival will be estimated using the Kaplan-Meier method, and 95% confidence intervals will be calculated using Greenwood's formula.

The frequency of subjects experiencing toxicities will be tabulated. Toxicities will be assessed and graded according to CTCAE v. 4.0 terminology. Exact 95% confidence intervals around the toxicity proportions will be calculated to assess the precision of the obtained estimates.

Imaging studies: The possibility of identifying sites of metastatic disease not apparent on conventional imaging (CT/MRI abdomen/pelvis, bone scan, and CXR) will be confirmed with serial imaging. Any potential metastatic site on J591 imaging will be followed over time by conventional imaging. Sites of disease appearing on J591 scan and subsequently confirmed by conventional imaging will be labeled as positive. Any site apparent on J591 scan that is subsequently biopsied as part of standard care and confirmed to be metastatic prostate cancer will be labeled as definite. Sites of disease appearing on J591 scan without any corroborating evidence (conventional imaging or biopsy) will be labeled as possible.

Adrenal hormonal levels: Baseline adrenal hormonal levels will be categorized by median baseline levels found in CALGB 9583 (60, 61). In addition, as this may be a different patient population, we will analyze by median as well as quartiles. We will correlate levels with time to radiographic metastatic disease as well as PSA response and overall survival. Changes in adrenal hormone levels will be analyzed with time (baseline, 1 month, 6 months, at progression).

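### The 95% CI for the difference in 18-month MFS is given as ±18 points, but the plan's own inputs give about ±27; ±18 matches an 80% interval

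*Combined protocol and SAP*

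**What the plan says.** Section 13.1 (Study Design/Endpoints) plans the primary comparison of 18-month MFS proportions as follows.

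- Patients: "With approximately 34 patients in the ketoconazole+J591 arm and 17 patients in the ketoconazole monotherapy arm (2:1 allocation").
- Rates: the control proportion "has been estimated to be 50" percent, and the combination "regimen is hypothesized to be 80" percent. The power sentence repeats them as "80% vs. 50%, respectively".
- Operating characteristics: the difference is to be detected "with $\geq 80\%$ power and a one-sided alpha level of 10" percent.
- Precision: "A 95% CI for the difference in the 18-month MFS proportion between the two treatment arms can be constructed to be within $\pm 18" percentage points of the true difference.

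The section says that the per-arm 95% intervals rest on binomial proportions. It names no interval method for the difference, and no other confidence level or pair of rates is attached to the ±18 figure.

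Section 13.4 makes a similar statement about PSA response: the 95% interval "will be within $\pm 9\%$ of the true value for Arm 1 and within $\pm 15\%$ of the true value for Arm 2". It gives no assumed response rate.

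**The concern.** A control arm of 17 patients with an expected proportion of 50% is very imprecise by itself. A difference that includes that arm must be less precise still, so ±18 points at 95% confidence looked too narrow for this design.

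This is the plan's only statement of precision for the primary effect. In a phase 2 trial of about 50 patients, the width of that interval governs how firmly an observed benefit can be read. A reader who relies on ±18 would expect a 30-point difference to exclude anything below +12 points. If the true half-width is near 27, the lower limit is only just above zero.

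**Working it through.** **Inputs (all from section 13.1).** n₁ = 34, p₁ = 0.80 (combination); n₂ = 17, p₂ = 0.50 (control); difference 0.30; one-sided alpha 0.10; stated 95% half-width 0.18.

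**Step 1. Confirm the inputs through the stated power.** The pooled proportion is (34 × 0.80 + 17 × 0.50)/51 = 0.70.

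- Null SE = sqrt(0.70 × 0.30 × (1/34 + 1/17)) = 0.1361.
- Alternative SE = sqrt(0.80 × 0.20/34 + 0.50 × 0.50/17) = sqrt(0.00471 + 0.01471) = 0.1393.
- Power = Φ((0.30 − 1.2816 × 0.1361)/0.1393) = 81.6%.

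This agrees with the stated minimum of 80%, so these are the inputs behind the design.

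**Step 2. Half-width of the interval for the difference (Wald), z × 0.1393.**

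| Confidence | z | Half-width (points) |
|---|---|---|
| 95% | 1.960 | 27.3 |
| 90% | 1.645 | 22.9 |
| 80% | 1.2816 | 17.9 |

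The stated ±18 does not reproduce at 95%. The confidence attached to exactly ±18 is 2Φ(0.18/0.1393) − 1 = 80.4%.

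**Step 3. Other methods and patient numbers, all at 95%.**

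| Method and n | Half-width (points) |
|---|---|
| Newcombe, 34/17 (limits +3.1 to +53.7) | 25.3 |
| Agresti-Caffo, 34/17 | 26.2 |
| Wald with pooled variance, 34/17 | 26.7 |
| Wald, maximum variance (50% in both arms), 34/17 | 29.1 |
| Wald, 33/17 | 27.4 |
| Wald, 37/18 (all 55 randomized) | 26.5 |
| Newcombe, 37/18 | 24.6 |

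**Step 4. Bounds.**

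- The control arm alone has a 95% half-width of 1.96 × sqrt(0.25/17) = 23.8 points. Adding the variance of an independent second arm can only widen this.
- Enumerating all outcomes under Binomial(34, 0.80) and Binomial(17, 0.50), the mean observed Wald 95% half-width is 26.6 points. The chance that it is 18 points or less is about 0.02%.
- A 95% half-width of 18 points at these rates and 2:1 allocation needs n₂ = (1.96/0.18)² × (0.25 + 0.16/2) = 39.1. That is about 40 control and 80 combination patients, or 120 evaluable against 51 planned.

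**Step 5. Effect on the interval at the design difference.**

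- As stated: 30 ± 18, or +12 to +48 points.
- Recomputed: 30 ± 27.3, or about +3 to +57 points (Wald); about +3 to +54 (Newcombe).

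**Step 6. Section 13.4.** Solving 1.96 × sqrt(p(1 − p)/n) = h shows when the stated widths hold.

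- ±9 with n = 34 requires a response rate of at most about 8% or at least about 92%.
- ±15 with n = 17 requires a rate of at most about 11% or at least about 89%.

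The documents' background gives two rates of roughly 50% or greater PSA decline with ¹⁷⁷Lu-J591. One is from the phase II trial ("Three pts achieved PSA declines of >50"%, of 32, or 9.4%) and the other from the phase I trial (4 of 35, or 11.4%). They give ±9.8 and ±10.7 at n = 34, and ±13.9 and ±15.1 at n = 17. Both trials tested the agent without this protocol's ketoconazole. For illustration only, an assumed rate anywhere from 20% to 80%, which is not in the documents, would give ±13 to 17 (n = 34) and ±19 to 24 (n = 17).

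**The case against.** The arithmetic is not in dispute; the objections concern weight and remedy.

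- **The sentence is descriptive.** No enrolment target, test or decision rule uses ±18, and the reported interval will be computed from the observed data. This stands: the error cannot carry into the trial's result. It is still a wrong statement about the primary comparison.
- **Patient numbers are approximate and no method is named.** This does not rescue the figure. At the design rates, the choices of method and n above leave a gap of about 7 to 11 points. A half-width of 18 or less with 34/17 needs extreme rates, for example 90% in both arms (17.5 points), which the plan does not assume.
- **The 80% match is only a numerical match.** This is fair. The multiplier 1.28 is also the critical value of the one-sided 10% test, so a carried-over multiplier is a plausible source, but the documents do not say so. The error stands whatever its origin.
- **The corrected number depends on the method and on n.** This stands and shapes the fix: both should be named alongside the number.
- **Section 13.4 is not a demonstrated error.** This stands. With low assumed rates the stated widths come close or are met, so what is missing there is the assumption.

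**Conclusion.** The stated precision of the primary difference is wrong. With 34 and 17 patients and true rates of 80% and 50%, the 95% half-width is 27.3 points (Wald), or 25.3 (Newcombe). With all 55 randomized patients split 37/18 it is 26.5 (Wald) or 24.6 (Newcombe). The stated ±18 is about one third too narrow and equals an 80% interval at the plan's inputs. The conclusion rests only on figures in section 13.1, and the same figures reproduce the stated power. Sample size, power and the test are unaffected.

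The section 13.4 half-widths can be neither confirmed nor refuted, because no response rate is given.

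**What to change.** In section 13.1, name the interval method for the difference and the patient numbers it refers to. Then restate the 95% half-width accordingly: about ±27 points for a Wald interval on 34/17, with 25 to 27 covering the choices above. Keeping ±18 and labelling it an 80% interval would also be arithmetically correct. It is the weaker option, because the plan uses 95% intervals for the per-arm proportions and the secondary endpoints.

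In section 13.4, state the PSA response rate assumed in each arm and recompute the two 95% half-widths from it.

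The cost is wording in these two sections and a less favourable statement of precision for the primary difference. Enrolment, power and the test do not change.
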